3. TRIAL DESIGN

Table 1: Trial Design

A	Study design	This is a first in man, open label, multi-centre, Phase I trial to investigate the safety, immunogenicity and patient survival following administration of the AST-VAC2 vaccine. Only one target dose (1×10^7 cells) will be explored. A reduced dose/administration schedule may be considered if required, based on emerging safety data.
B	Patient group	Patients with advanced NSCLC.
C	Sample size	Approximately eight patients will be entered into this trial. The final number will depend on emerging safety data, the number of patient replacements required and vaccine availability.
D	Study intervention	
Patients will receive six AST-VAC2 vaccinations, administered weekly over six weeks.
 
They will attend an end of vaccination visit 30 days after their last AST-VAC2 vaccination, and attend follow-up visits up to 12 months after their first AST-VAC2 vaccination. After which, patients will be followed up for safety quarterly by telephone for five years (post first vaccination). Information on OS will be collected for up to 2 years after the first vaccination for all patients or until all patients have died, whichever event occurs first.

E	Study analysis	
Safety evaluations will be conducted after the first patient has received AST-VAC2 and then again after the second and third patients have been treated. Once open recruitment has been initiated, safety review will be performed at regular intervals (as required). A safety review committee, consisting of all Investigators, representatives of the Sponsor and representatives of the drug company (observers only), will review emerging study data, with particular reference to ensuring that patients are able to complete the vaccination schedule without AST-VAC2 toxicity-related delays. See protocol Section 3.3.2.
 
An interim analysis will be conducted once all patients administered AST-VAC2 have withdrawn, died or completed their 2-year follow-up visit for survival. Once this condition is met, a data cut-off will be established. All patient visits occurring on or before this date will be analysed and summarised in the clinical study report, including safety data to date and assessment of OS at 2 years.
 
Any data collected after this date will be summarised in a supplemental report for the final analysis to satisfy the safety reporting requirements for AST-VAC2 as an advanced therapy investigational medicinal product (ATIMP).
 
The final analysis will be conducted after one of the following conditions is met:
 
 • The trial is terminated early, e.g. due to toxicity; • The End of Trial has been reached (when all patients have either withdrawn from the trial or died, or the last patient

		
has completed their final follow-up visit [whichever is the latter]).
 
Once one of these conditions is met, a data cut-off will be established. All patient visits occurring on or before this date will be analysed and summarised in a supplemental report.
 
Due to the small sample size, there are no formal statistical analyses planned for this trial.

F	Dose escalation schedule	There is no dose escalation schedule for this study, only one dose will be explored. Stopping rule criteria can be found in protocol Section 3.3.3.

For full details of the trial design, background and rationale for the study, please refer to the current study protocol.

4. PATIENT POPULATION AND ENDPOINTS

Patients must fulfil all the inclusion/exclusion criteria to be eligible for entry to the trial. Refer to the study protocol for the complete list of inclusion and exclusion criteria.

4.1 Patient Populations

The analysis sets are defined as follows:

Full Analysis Population (FAP): All patients who enrolled onto the main trial.
Patients who are enrolled in error onto the main trial (due to ineligibility/administrative error), prior to receiving any AST-VAC2 vaccinations, will be excluded from the FAP.

Safety Population: All enrolled patients who received at least one AST-VAC2 vaccination.
This population will also be used for overall survival at 2 years post first AST-VAC2 vaccination. Patients are evaluable for survival regardless of whether they go on to receive another anti-cancer therapy.

HLA Population: All patients who had a sample taken for HLA analysis.
[Redacted]

Secondary Immunogenicity Endpoint Population: All eligible patients who received at least three AST-VAC2 vaccinations and have had a baseline blood sample and at least two post-vaccination blood samples taken.
[Redacted]

Response Population: All eligible patients who have received at least one AST-VAC2 vaccination and have had a baseline assessment of disease and at least one repeat disease assessment measured according to irRC. For details of irRC, refer to Appendix 3 of the study protocol.
If rapid tumour progression occurs before completion of the scheduled six AST-VAC2 vaccinations, the patient will be classified as having early progression. Patients with early progression will be included in the response population.

5. DATA CONVENTIONS AND GENERAL ANALYSIS

5.1 Patient disposition

Patients excluded from any population (defined in Section 4.1) will be detailed.

The accrual and trial discontinuation details will be presented descriptively. This should include details of:

- Screening failure patients
 - Pre-screening – patients were pre-screened for human leucocyte antigen (HLA) status as part of the study. The number of patients who underwent HLA screening and the number of patients HLA A*02:01 positive and negative will be summarised.
 - Overall screening failure information is available via the e-screening logs and will be described descriptively.
- Information on ineligible patients who were enrolled and/or received AST-VAC2.
- Reasons for vaccination discontinuation by number of vaccinations received will be described by counts and percentages. Reasons for vaccination discontinuation other than disease progression will be detailed and summarised separately (Section 5.3).

5.2 Baseline characteristics

Demographics and baseline characteristics will be summarised for all enrolled patients.

Table 2: Summary of Patient Demography (*Full Analysis Population*)

	All Patients N=X
Patients	
Sex	
Male	N (%)
Female	
Age (Years)	
Mean	
Median	
Min	
Max	
WHO performance status	
0	N (%)
1	
2	
3	
4	

*Footnote: [REDACTED] withdrew from the study prior to first vaccination

In case of pre-treatment characteristics with multiple measurements per patient before the start of treatment (laboratory assessments, vital signs), the baseline measurement will be considered the last value prior to or on the first day of vaccination.

Baseline performance status assessments will be summarised with frequency counts.

For the cancer history, histologic diagnosis, number of baseline lesions, and involvement in the different sites will be summarised. If incomplete dates are recorded, the rules described in Section 5.10 will be used for imputation.

The primary tumour sites and baseline lesions will be recorded in order to categorise them accurately in the analysis.

A frequency tabulation of the different types of previous oncologic surgery (excluding only diagnostic or palliative procedures), radiotherapy, or anti-cancer systemic therapy will be given.

Table 3: Primary Diagnosis at Baseline (*Full Analysis Population*)

	No. of Patients (N=XX)
Primary tumour type	
	N (%)
Stage at study entry	
Stage I	
Stage II	
Stage III	
Stage IV	
Not applicable	
Not known	

Table 3 will be manually generated for the Clinical Study Report (CSR) based on the programmed table from the clinical trial database to allow for better grouping by primary tumour type.

Table 4: Summary of Prior Treatment for Malignant Disease (*Full Analysis Population*)

	No. of Patients (N=XX)
Prior treatment	
Surgery	N (%)
Radiotherapy	
Chemotherapy/other	

Table 5: Summary of Prior Lines of Chemotherapy/Other Therapy (*Full Analysis Population*)

	No. of Patients (N=XX)
Lines of chemotherapy/other	
1	N (%)
2	
3	
4	
5, etc	
Median (range)	X (X-X)

Table 5 will be manually generated for the Clinical Study Report based on the 'Previous Treatment for Malignant Disease – Chemotherapy/Other Therapy' listing.

Table 6: Summary of Baseline Disease Sites (*Full Analysis Population*)

Baseline disease type	No. of Patients (N=XX)	Patient Numbers
Primary tumour	N (%)	XX/XXX, XX/XXX
Local recurrence		
Regional nodes		
Metastatic nodes		
Lung metastases		
Liver metastases		
Etc		

5.3 Patient withdrawal

Reasons for patient withdrawal from vaccination will be provided as the data are available and will be presented descriptively.

5.4 Protocol deviations

A protocol deviation is defined as any departure from what is described in the protocol of a clinical trial approved by an Independent Ethics Committee and Competent Authorities. Therefore, it applies to deviations related to patient inclusion and clinical procedures (e.g. assessments to be conducted or parameters to be determined), and also to other procedures described in the protocol that concern the Good Clinical Practice (GCP) guidelines or ethical issues (e.g. issues related to obtaining the patients' Informed Consent, data reporting, the responsibilities of the Investigator, etc.).

Protocol deviations are captured throughout the trial open phase on the Sponsor's central tracker and can be filtered by study and by deviation category or on the study specific pharmacokinetic/pharmacodynamic (PK/PD) deviations tracker (and the PK/PD tab [version 1] of the standard study tracker for deviations prior to set up of PK/PD deviations tracker). Standard deviation categories have been defined by the Sponsor and are further defined by those which are deemed reportable (important deviations) in the CSR. Those deviations which have been coded as CSR reportable

Vaccination could be delayed if one or more adverse events (excluding injection site reactions) related to AST-VAC2 (highly probably, probably or possibly related) are still present, have not resolved to Grade ≤ 1 and are considered by the Investigator to be clinically significant and a clear contraindication to vaccination. In those instances, vaccination should be delayed for up to 2 weeks until the adverse events (AEs) have recovered to Grade ≤ 1 . Patients who require a dose interruption of greater than 2 weeks will be reviewed on a case-by-case basis to determine if the patient should be withdrawn from the trial.

Any delays, reductions or omissions to the vaccination schedule will be summarised. The reasons for the dose modifications will be detailed.

A patient is considered to have completed vaccination if the response to 'Did the subject complete 6 vaccinations?' is 'Yes'. Treatment compliance and any treatment modifications will be reported descriptively.

5.6 Safety

Descriptive statistics will be used for evaluation of safety. The incidence and grade of AEs and laboratory abnormalities will be calculated considering the most severe grade per patient and will be displayed in frequency tables using counts and percentages.

Deaths and serious adverse events (SAEs) and events resulting in vaccination discontinuation will be described.

Additional safety analyses may be determined at any time, in order to most clearly enumerate rates of toxicities and to further define the safety profile of AST-VAC2.

Other safety parameters (vital signs, physical examination, electrocardiograms and World Health Organisation [WHO] performance status) will be presented in the data listings.

- The Safety Population is composed of all patients that receive at least one AST-VAC2 vaccination. The Safety Population will be used for the general safety presentations.
- Events will be coded and classified according to the Medical Dictionary for Regulatory Activities (MedDRA; the version used will be shown as a footnote on the AE listing). Toxicity evaluation (grading) will be made according to NCI CTCAE version 4.02 except for ISRs, which have a study specific grading system (please refer to Protocol Section 9.8).
- As far as all the toxicities are concerned (except for ISRs), the NCI CTCAE grade will be used wherever an NCI CTCAE grading exists. For summary tables, the protocol-specific grading for ISRs will be mapped to the CTCAE grades, in order to summarise all the AEs (see below).
- As a convention, the term "Grade" will always be used. Toxicities will be described according to the maximum NCI CTCAE grade or, for ISRs which do not form the subject of NCI CTCAE classification, according to protocol-specific grade.
- Maximum CTCAE grade for all AEs will be captured.

Protocol-specific grading for ISRs	CTCAE grade	Label used in summary tables
Grade 1	Grade 1	Grade 1
Grade 2	Grade 2	Grade 2
Grade 3	Grade 3	Grade 3
Grade 4	Grade 4	Grade 4

5.7 Adverse Events

Pre-treatment AEs will be defined as those where “Did this AE start prior to first vaccination?” is ticked. Treatment Emergent AEs (TEAEs) will be defined as those where “Did this AE start prior to first vaccination?” is not ticked.

Related AEs are those where causality to IMP is considered to be Possible, Probable or Highly Probable.

The frequency of adverse events will be summarised overall. A patient can be counted multiple times per row for the No. of Episodes but will only be counted once per row for the No. of Patients.

Table 8: Frequency of All Adverse Events (*Safety Population*)

SYSTEM ORGAN CLASS Preferred Term	No. of Episodes Reported	No. of Patients N=XX
All AEs	N	N (%)
BLOOD AND LYMPHATIC...		
Anemia		
CARDIAC DISORDERS		
Sinus tachycardia		
Etc		

There will be additional versions (as required) of the above table based on pre-treatment AEs, TEAEs, treatment emergent SAEs (any AE that is considered Serious) and related TEAEs.

Overview of TEAEs will be presented for all patients. An AE is considered to have led to withdrawal if an adverse event with “Did the AE cause the subject to be discontinued from the study?” is recorded as yes.

Table 9: Overview of Treatment Emergent Adverse Events (*Safety Population*)

Patients with TEAEs	Overall No. of Patients N=XX
Patients with ≥ 1 TEAE	N (%)
Patients with ≥ 1 TE SAE	
Patients with ≥ 1 related TEAE	
Patients with ≥ 1 CTCAE Grade 3, 4 or 5 TEAE	
Patients with ≥ 1 AE leading to withdrawal*	
Patients who died due to TEAE	

*Footnote: AEs that lead to withdrawal of vaccination; patients remained on study for assessment of response, safety and overall survival.

TEAEs leading to withdrawal of vaccination will be summarised descriptively. Patients will be included if an AE has “Action taken” recorded as “Drug Withdrawn” or “Did the AE cause the subject to be discontinued from the study?” is recorded as yes.

All TEAEs and related TEAEs by worst CTCAE grade within an episode will be presented by number of TEAEs and by number of patients (see Table 10 and Table 11, respectively).

Table 10: Frequency of Treatment Emergent Adverse Events and Related Treatment Emergent Adverse Events by Worst CTCAE Grade within an Episode (*Safety Population*)

SYSTEM ORGAN CLASS Preferred Term	All TEAEs						AST-VAC2 Related TEAEs					
	Grade						Grade					
	Total	1	2	3	4	5	Total	1	2	3	4	5
Overall total	N	N	N	N	N	N	N	N	N	N	N	N
BLOOD AND LYMPHATIC...												
Anaemia												
CARDIAC DISORDERS												
Sinus tachycardia												
Etc												

Table 11: Frequency of Patients with Treatment Emergent Adverse Events and Related Treatment Emergent Adverse Events by Worst CTCAE Grade within an Episode (*Safety Population*)

SYSTEM ORGAN CLASS Preferred Term	All TEAEs						AST-VAC2 Related TEAEs					
	No. of patients with ≥ 1 AE (N=XX)						No. of patients with ≥ 1 AE (N=XX)					
	Grade						Grade					
	Total	1	2	3	4	5	Total	1	2	3	4	5
Overall total	N (%)	N	N	N	N	N	N (%)	N	N	N	N	N
BLOOD AND LYMPHATIC...												
Anaemia												
CARDIAC DISORDERS												
Sinus tachycardia												
Etc												

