#### 4.1.2 Exclusion criteria

1. Radiotherapy (except for palliative reasons) during the previous four weeks before treatment.
2. Ongoing toxic manifestations of previous treatments greater than CTCAE Grade 1. Exceptions to this are alopecia or certain Grade 2 toxicities, which in the opinion of the Investigator should not exclude the patient. If there is uncertainty over whether the toxicity should exclude the patient, the Sponsor should be consulted.

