### 9.2 Adverse event definitions

#### 9.2.1 Adverse event

Adverse events for this trial will be graded according to NCI CTCAE version 4.02. In addition, Injection Site Reactions will be graded according to protocol specific grading system as per [Section 9.8](#).

An adverse event (AE) is any untoward, undesired or unplanned medical occurrence in a patient administered an IMP, a comparator product or an approved drug.

An AE can be a sign, symptom, disease, and/or laboratory or physiological observation that may or may not be related to the IMP or comparator.

An AE includes but is not limited to those in the following list.

- A clinically significant worsening of a pre-existing condition. This includes conditions that may resolve completely and then become abnormal again.
- AEs occurring from an overdose of an IMP, whether accidental or intentional.
- AEs occurring from lack of efficacy of an IMP, for example, if the Investigator suspects that a drug batch is not efficacious or if the Investigator suspects that the IMP has contributed to disease progression.

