### 9.3.3 Eligible patients

For eligible patients, SAE and AE collection and monitoring will commence at the time the patient gives their written consent to participate in the trial by signing the main trial consent form and will continue until 30 days after the last vaccination (administration of IMP). From this time point until the patient withdraws, dies or completes the trial, new or ongoing AST-VAC2-related AEs will be collected (regardless of whether the patient goes on to other anti-cancer therapies).

Should an Investigator become aware of any AST-VAC2 -related SAEs after the patient has completed the protocol-mandated follow-up period (as specified above), these must also be reported to the Sponsor within the expedited timelines in Section 9.4.

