AE assignment: AE is assigned to the vaccination number it begins in. This is regardless of whether the AE start time shows the AE started before the dose that day. The only exception is for the first vaccination; if 'Did AE occur prior to first dose' is checked then no vaccination number will be assigned.

Duration of treatment: this is from the day of the first vaccination until the day of the final vaccination. Duration of treatment will be described using summary statistics.

Completed vaccination: AST-VAC2 vaccinations are to be given once a week for 6 weeks. A patient is considered to have completed vaccination when vaccination data entered is for each of those expected weekly visits (despite dose modifications).

Treated patients: If the drug administration form in the eCRF has the 'date of vaccination' completed, this constitutes a treated patient.

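### SAP 5.7 defines treatment-emergent AEs by start date alone, so an AE logged between consent and first vaccination that later worsens is left out of the treatment-emergent tables

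*SAP*

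**What the plan says.** SAP 5.7 splits all AEs in two with a single eCRF box. One half reads "Pre-treatment AEs will be defined as those where “Did this AE start prior to first vaccination?” is ticked"; the other reads "Treatment Emergent AEs (TEAEs) will be defined as those where “Did this AE start prior to first vaccination?” is not ticked". Grade, seriousness and causality play no part in the split.

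Three further conventions bear on an AE whose grade changes:

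- SAP 5.7, on the graded tables: "All TEAEs and related TEAEs by worst CTCAE grade within an episode will be presented by number of TEAEs and by number of patients".
- SAP 5.6: "Maximum CTCAE grade for all AEs will be captured".
- SAP 5.10, on assigning AEs to vaccinations: "if 'Did AE occur prior to first dose' is checked then no vaccination number will be assigned".

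The protocol opens the AE record before dosing. Under 9.3.3, "SAE and AE collection and monitoring will commence at the time the patient gives their written consent to participate in the trial", and 7.1.2 allows consent more than 28 days before the first vaccination. Patients may enter with some residual toxicity; after a general Grade 1 limit, exclusion criterion 2 in 4.1.2 adds "Exceptions to this are alopecia or certain Grade 2 toxicities, which in the opinion of the Investigator should not exclude the patient". Section 7.1.2 collects concomitant conditions and baseline signs and symptoms as medical history, and 9.2.1 lists as an AE "A clinically significant worsening of a pre-existing condition".

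**The concern.** Safety is the primary endpoint, and it is defined by frequency, causality and severity together. In the planned CSR outputs, Tables 10 and 11 are the only summary tables that cross grade with relatedness across all AE terms, and both are limited to treatment-emergent events. Protocol 13.4 asks for frequency tables by worst grade, showing related and unrelated events, without that limit.

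A start-date rule with no worsening limb files a post-vaccination deterioration under the period before vaccination. If an AE that began in screening flares after dosing and is judged possibly related, its grade and causality reach none of the tables a reader would use to judge the vaccine. The rule can remove such events from the treatment-emergent tables but cannot add any, so the error runs one way.

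**Working it through.** The plan gives no figure that depends on this definition, and SAP Table 1 states that no formal statistical analysis is planned. The check is therefore to apply the rule to records and then size one misfiled patient.

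**1. Apply the rule to illustrative records.** "Ticked" is replaced here by yes/no for a start before first vaccination. The comparison rule adds worsening in grade after first vaccination.

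| Record | Start before first vaccination | TEAE under SAP 5.7 | TEAE with worsening limb |
|---|---|---|---|
| Screening AE, Grade 1, reaches Grade 3 after vaccination | yes | no | yes |
| Screening AE, Grade 1, stays Grade 1 | yes | no | no |
| AE starting after vaccination, Grade 3 | no | yes | yes |
| Medical-history condition that worsens to a clinically significant degree after vaccination (new AE under protocol 9.2.1) | no | yes | yes |

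Only the first row changes.

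**2. Trace that first record through the outputs** (SAP 5.6 to 5.8.2, 6.1, 6.2, 7.5).

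- Absent: Tables 10 and 11 (CSR 14.3.7, 14.3.8); the versions of Table 8 for TEAEs, treatment-emergent SAEs and related TEAEs (CSR 14.3.4 to 14.3.6); and the treatment-emergent rows of Table 9 (CSR 14.3.1), unless the patient has another qualifying event.
- Present: Table 8 for all AEs (CSR 14.3.2) and its pre-treatment version (CSR 14.3.3), neither of which has a grade or causality column; the AE listings; the descriptions of SAEs, deaths and stopping-rule events where they apply; and ClinicalTrials.gov Outcome Measure 1, which counts from consent without the treatment-emergent filter.

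The posted count of related Grade 3 or higher events could then exceed what the CSR's graded tables show, although SAP section 7 says the two will be consistent.

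**3. Size of one affected patient.** Protocol 1.6 gives up to eight patients. For a Table 9 row in which the patient has no other qualifying event:

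- Under SAP 5.7: 0/8 = 0.0%. Exact 95% upper limit = 1 − 0.025^(1/8) = 1 − 0.631 = 36.9%.
- With the worsening limb: 1/8 = 12.5%. Exact (Clopper-Pearson) 95% interval 0.3% to 52.7%.
- Difference: 12.5 − 0.0 = 12.5 percentage points.

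If only six were treated (an assumption, since the documents give only the maximum):

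- 0/6 = 0.0%, upper limit 1 − 0.025^(1/6) = 45.9%.
- 1/6 = 16.7%, interval 0.4% to 64.1%.
- Difference: 16.7 percentage points.

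The intervals are given for scale only; the SAP does not plan them.

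**The case against.** The strongest reply is that most of the exposure is already covered. Residual toxicity at entry is collected as medical history and baseline signs and symptoms, and its clinically significant worsening is a new AE under protocol 9.2.1. That AE starts after vaccination, so it is treatment-emergent. This stands. A reader might infer from the entry criteria that any permitted baseline toxicity that worsens is lost; the documents do not support that. The gap is confined to events first logged as AEs between consent and first vaccination.

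Second, a reader might infer that the event disappears from safety reporting. It does not, as step 2 shows. Related events that meet the stopping criteria in protocol 3.3.3 must also be reported as SAEs and go to independent review. What remains is that no CSR summary table across AE terms shows the event's grade and relatedness. SAP 5.6 does promise frequency tables by most severe grade in general terms, but the list in SAP 6.2 contains none for all AE terms that is not limited to TEAEs.

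Third, sites may already be told to open a new record when an AE worsens. Such instructions would normally sit in eCRF completion guidance or a data management plan, which are not among the documents. This is a fair limit on certainty. The worst-grade-per-episode convention points the other way, though it does not define an episode, and a primary-endpoint classification should not depend on an unstated convention.

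Fourth, the 12.5 points need a patient with no other qualifying event. Protocol 3.3.1 expects injection-site inflammation as the main toxicity, so the related-TEAE row may count the patient anyway. This stands for that row; it is a weaker answer for the Grade 3 to 5 row.

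**Conclusion.** The point holds in a narrow form and should be fixed. Under SAP 5.7, an AE recorded between consent and first vaccination, ongoing at that vaccination and worse afterwards is classed as pre-treatment and left out of every treatment-emergent table. Each such patient with no other qualifying event lowers a Table 9 row by 12.5 percentage points at eight patients, always towards a more favourable profile.

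This assumes that a worsened AE stays in its original record, which the grading convention suggests but neither document states outright. How many patients are affected cannot be known from the documents. A reader might think it likely in pretreated advanced NSCLC, but no figure in either document supports a rate.

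**What to change.** In SAP 5.7, define a TEAE as an AE that starts on or after first vaccination, or that starts before it and afterwards worsens in grade, becomes serious or becomes related to AST-VAC2.

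Tell sites to enter a post-vaccination worsening of an open AE as a new record with its own start date, grade and causality.

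For data already entered, query every ticked AE that was still ongoing at first vaccination. Filtering the listing on when the maximum grade was reached may not work, because neither document says that date is captured.

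The cost is a short SAP amendment, a note to sites and a few data queries in a trial of up to eight patients. TEAE counts may come out slightly less favourable.

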#### 5.3.2 Dose delays & interruptions

If at the time of the next scheduled vaccination day, one or more adverse events (AEs) (excluding ISRs) related to the AST-VAC2 vaccine (highly probably, probably or possibly related) are still present, have not resolved to Grade  $\leq 1$  and are considered by the Investigator to be clinically significant and a clear contraindication to vaccination, the next vaccination day should be delayed for up to two weeks until the AE(s) have recovered to this level. In case of uncertainty, individual cases should be discussed with the Sponsor. Patients who require a dose interruption of greater than two weeks will be reviewed on a case by case basis to determine whether the patient should be withdrawn from the trial. The Sponsor will confirm whether an extended interruption is acceptable or if the patient should be withdrawn from further trial treatment.

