## CONFIDENTIAL

If the patient is administered a COVID-19 vaccination during the AST-VAC2 vaccination period, there should be a 48 hours interval between the two vaccinations and they should be administered to different sites. The AST-VAC2 vaccination should be delayed as needed to accommodate this interval.

If the patient is withdrawn from further trial treatment, follow up information and post vaccination research blood [REDACTED] sampling will still be applicable unless the patient withdraws consent from further follow up and participation in the trial or if the Sponsor advises that further sampling is not required.

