## 11 PATIENT WITHDRAWAL BEFORE COMPLETION OF TREATMENT SCHEDULE

AST-VAC2 has been classified as an ATIMP therefore extended follow up (up to five years post first vaccination) is applicable for all patients who receive the IMP.

The Investigator must make every reasonable effort to keep each patient on trial for the whole duration of the trial in order to collect long term safety and pharmacodynamic data. However, if the Investigator removes a patient from the trial (prior to completion of the vaccinations) or if the patient declines further participation, final assessments (as per the 'End of Vaccination' visit), should be performed ideally before any subsequent therapeutic intervention. All the results of the evaluations and observations, together with a description of the reasons for withdrawal from the trial, must be recorded in the patient's medical records and in the eCRF.

A patient may stop vaccination due to AEs but would not be withdrawn from the trial and would continue for follow-up of safety, survival and tertiary endpoints unless they withdraw.

The following are justifiable reasons for the Investigator to withdraw a patient from the trial.

- Withdrawal of consent.
- Serious deviation from the trial protocol (including persistent patient attendance failure and persistent non-compliance).
- Sponsor's decision to terminate the trial.
- Withdrawal by the Investigator for clinical reasons not related to AST-VAC2.
- Loss to follow up.

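### The rule that fills the SAP Table 9 row on AEs leading to withdrawal and the row's own footnote describe different patients

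*SAP*

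**What the plan says.** Three statements in SAP Section 5.7 bear on this row, and they stand within a few lines of each other.

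- **The rule, directly before Table 9.** The sentence begins "An AE is considered to have led to withdrawal if an adverse event with" and is completed by a yes to the eCRF question on whether the AE caused the subject to be discontinued from the study. No other condition is given.
- **The footnote to the row.** It explains the row as "AEs that lead to withdrawal of vaccination; patients remained on study for assessment of response, safety and overall survival".
- **The paragraph after Table 9.** It says "TEAEs leading to withdrawal of vaccination will be summarised descriptively". A patient enters this summary if *Action taken* is *Drug Withdrawn*, or if the study-discontinuation question is answered yes.

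The protocol keeps the two kinds of withdrawal apart. Section 11 states: "A patient may stop vaccination due to AEs but would not be withdrawn from the trial". Section 5.3.2 has a sentence beginning "If the patient is withdrawn from further trial treatment, follow up information and post vaccination research blood", which goes on to keep these activities running unless consent is withdrawn or the sponsor advises that further sampling is not required. SAP Section 6.2 lists Table 9 as CSR Table 14.3.1, the overview of treatment-emergent AEs in the Safety Population.

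**The concern.** Safety and tolerability is the primary objective, and this is the only Table 9 row on withdrawal because of an AE. Protocol Section 11 provides for a patient to stop vaccination for an AE and continue in follow-up. The rule as written does not select that patient, while the footnote tells the reader that such patients are exactly who is counted. A programmer who follows the rule and prints the footnote produces a row whose caption misdescribes its content. The same CSR could then show one count in the overview and another in the descriptive summary, with nothing to explain the difference.

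**Working it through.** The documents state no figure on this point, so there is nothing to reproduce. The check is to apply the three definitions to the same records.

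**Inputs.** D = *Action taken* is *Drug Withdrawn*. S = the study-discontinuation question is answered yes. Both fields are named in SAP 5.7. The footnote is read literally as vaccination withdrawn and the study not discontinued.

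| D | S | Table 9 rule (S) | Footnote (D and not S) | Paragraph after Table 9 (D or S) |
|---|---|---|---|---|
| no | no | no | no | no |
| no | yes | yes | no | yes |
| yes | no | no | yes | yes |
| yes | yes | yes | no | yes |

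The rule needs S = yes and the footnote needs S = no, so no record is selected by both. The Protocol Section 11 case is the third line (D = yes, S = no). The footnote and the later paragraph select it; the Table 9 rule does not.

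**Scale.** Protocol Section 1.6 plans up to eight patients. With N = 8 treated, one patient is 100/8 = 12.5 percentage points. Suppose, as an assumption, that k of the eight stop vaccination for an AE and stay on study, and that nobody leaves the study for an AE:

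| k | Table 9 rule, field answered literally | Footnote meaning |
|---|---|---|
| 1 | 0/8 = 0.0% | 1/8 = 12.5% |
| 2 | 0/8 = 0.0% | 2/8 = 25.0% |
| 3 | 0/8 = 0.0% | 3/8 = 37.5% |

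If sites instead answered yes to the study question whenever vaccination stopped for an AE, the rule also returns k/8 and nobody is missed. The shortfall therefore lies between 0 and k patients, and the documents do not give k.

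**The case against.** The strongest reply is that these patients are not lost from the report, and that reply stands. The paragraph after Table 9 picks them up through *Drug Withdrawn*. SAP 5.1 plans counts and percentages of reasons for stopping vaccination, by number of vaccinations received. SAP 5.6 describes events that led to vaccination being discontinued. The participant flow in SAP 7.2 counts patients who did not complete six vaccinations and offers an adverse event as a reason. A reader might infer that AE-related vaccination stops go unreported; the documents do not support that. The defect is confined to one row and to its agreement with the text around it.

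A second reply is that sites may have used the study question to record vaccination stops, with the footnote there to say so. This is plausible, because the protocol's wording is itself loose. Section 5.3.2 reviews patients with an interruption of more than two weeks "to determine whether the patient should be withdrawn from the trial", and its next sentence describes the decision as withdrawal from further trial treatment. No document states such a convention, however, and the paragraph after Table 9 treats the two fields as separate. If it is the convention, the SAP should say so.

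A reader might also infer that the row must come out at zero. That does not follow. The row is not limited to related AEs, and Section 11 allows "Withdrawal by the Investigator for clinical reasons not related to AST-VAC2", so an unrelated AE can lead to discontinuation from the study. Section 5.3.2 also leaves trial withdrawal open after a long interruption.

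Finally, the trial is descriptive and no registry outcome measure uses this row. That lowers the priority; it does not make the footnote agree with the rule.

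**Conclusion.** The wording conflict is certain: on a literal reading, the rule and the footnote of this row do not overlap, and the patient described in Protocol Section 11 falls outside the rule. CSR Table 14.3.1 can therefore understate AE-related withdrawal of vaccination and disagree with the descriptive summary. Whether any patient is actually miscounted is not known. It depends on how sites answered the study-discontinuation question, and the eCRF guidance is not in the documents. Each affected patient is worth 12.5 percentage points if eight are treated, and the number may be zero. Because the same patients are captured elsewhere in aggregate and no formal analysis uses the row, the severity is minor.

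**What to change.** Replace the single Table 9 row with two:

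- **(a) TEAE leading to withdrawal of vaccination.** *Action taken* is *Drug Withdrawn*, limited to patients whose answer to the eCRF question "Did the subject complete 6 vaccinations" (SAP treatment compliance text) is not yes. The limit keeps out a patient whose AE followed the sixth vaccination.
- **(b) TEAE leading to discontinuation from the study.** The study-discontinuation question is answered yes.

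A patient who stops vaccination for an AE and stays in the trial then appears in (a) only. One who completes six vaccinations and later leaves the study for an AE appears in (b) only. One who stops vaccination early for an AE and also leaves the study for it appears in both.

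Before database lock, review records with study discontinuation = yes, six vaccinations not completed and no *Drug Withdrawn*. Compare them with the recorded reason for stopping vaccination, and add to (a) those where the AE was the reason.

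Use the same two definitions in the paragraph after Table 9. Its present either-or rule would also count, as a withdrawal of vaccination, a patient who had completed all six and left the study later. Remove from the footnote the blanket statement that patients remained on study.

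The cost is SAP wording, one extra table row, a few lines of code and a short pre-lock check, using information already recorded. No clinical rule changes.
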